10.4 Description of statistical methods

10.4.1 General Approach

For all variables of interest, percent change will be evaluated for statistical significance by Unpaired T-test or Mann-Whitney U-test as appropriate. Statistical significance will be set at $P < 0.05$.

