10.1 Statistical and Analytical Plans

An a priori power analysis was conducted using G*Power v3.1.9.2 to determine the minimum sample size required to find significance with a desired level of power set at 0.80 and alpha (a) level at 0.05. Based on this analysis, it was determined that a minimum of 205 participants were required to ensure adequate power for a Pearson's Chi-square Test of Independence. (12, 13, 14) (Appendix L)

Each participant will be required to take an enrollment survey that collects information on race, ethnicity, and socio-economic status. Participant's addresses will be obtained as part of the requisition process for the CLIA lab, from which information on geographic location can be obtained. In addition to the factors listed above, the enrollment survey also collects information on status and type of health insurance, reproductive health, breast health knowledge, prior screening history, and family and personal history of cancer.

The exit survey has been designed to collect information on the participant experience with Melody® and comprehension of the information Melody® relayed through their site clinician. In addition, information is collected on participant's intention to schedule/participate in future screening mammograms and/or change in intention to participate in a previously scheduled screening mammogram.

Data will be analyzed using SPSS Statistics software. To determine the presence of significant changes, Unpaired T-tests or Mann-Whitney U-test will be used with a significance level set at P < 0.05.

Due to the effect of COVID-19 on screening rates, screening mammogram participation rates will be compared to rates reported for the state of Arkansas in 2019.

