10.2 Statistical Hypothesis

Primary endpoint:

- H_0 = Participation rates in yearly screening mammography with the incorporation of Melody® (examined by geographic location, socio-economic status, race, and ethnicity) will not be greater than participation rates recorded in 2019.
- H_1 = Participation rates in yearly screening mammography with the incorporation of Melody® (examined by geographic location, socio-economic status, race, and ethnicity) will be greater than participation rates recorded in 2019.

Secondary endpoint:

- H_0 = Participation rates in yearly screening mammography, with the incorporation of Melody® (examined by clinical sites), will not be greater than participation rates recorded

in 2019.

- H_0 = Participation rates in yearly screening mammography, with the incorporation of Melody® (examined by clinical sites), will not greater than participation rates recorded in 2019.

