10.3 Analysis Datasets

Primary endpoint datasets will be broken down by classifications outlined in the table below.

Primary Endpoint Characteristic

Ethnicity	Hispanic
	Non-Hispanic
Race	American Indian-Alaska Native
	Asian
	Black or African American
	Native Hawaiian or Other Pacific Islander
	White
Socio-economic status	\$35,000 or less
	\$35,000-\$80,000
	\$80,000-\$130,000
	\$130,000-\$200,000
	\$200,000 or higher
Geographic Location	Metropolitan
	Nonmetropolitan

Analysis of secondary endpoint datasets will be analyzed by comparing screening mammography participation rates reported by the clinical site from 2019 to screening mammography participation rates observed after the study.

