10.4.2 Analysis of primary efficacy endpoints

Data for primary efficacy endpoints will be presented as follows:

Analysis of Primary Efficacy Endpoints

		VIOLA	2019	Total
Ethnicity	Hispanic	N (% of total for VIOLA)	N (% of total for 2019)	N (% of total)
	Non-Hispanic	N (% of total for VIOLA)	N (% of total for 2019)	N (% of total)

P value		P =?		
Race	American Indian-Alaska Native	N (% of total for VIOLA)	N (% of total for 2019)	N (% of total)
	Asian	N (% of total for VIOLA)	N (% of total for 2019)	N (% of total)
	Black or African American	N (% of total for VIOLA)	N (% of total for 2019)	N (% of total)
	Native Hawaiian or other Pacific Islander	N (% of total for VIOLA)	N (% of total for 2019)	N (% of total)
	White	N (% of total for VIOLA)	N (% of total for 2019)	N (% of total)
P value		P =?		
Socio-economic status	\$35,000 or less	N (% of total for VIOLA)	N (% of total for 2019)	N (% of total)
	\$35,000-\$80,000	N (% of total for VIOLA)	N (% of total for 2019)	N (% of total)
	\$80,000-\$130,000	N (% of total for VIOLA)	N (% of total for 2019)	N (% of total)
	\$130,000-\$200,000	N (% of total for VIOLA)	N (% of total for 2019)	N (% of total)
	\$200,000 or higher	N (% of total for VIOLA)	N (% of total for 2019)	N (% of total)
P value		P =?		
Geographic Location	Metropolitan	N (% of total for VIOLA)	N (% of total for 2019)	N (% of total)
	Nonmetropolitan	N (% of total for VIOLA)	N (% of total for 2019)	N (% of total)
P value		P =?		

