10.4.3 Analysis of the Secondary Endpoints

Analysis of the secondary endpoints will be presented as follows:

Analysis of Secondary Endpoints				
		VIOLA	2019	Total
Site 1	Followed through with screening mammogram	N (% of total for VIOLA)	N (% of total for 2019)	N (% of total)
	Did not follow through with screening mammogram	N (% of total for VIOLA)	N (% of total for 2019)	N (% of total)
P value		P =?		

The analysis will be conducted for each site enrolled in the VIOLA Study.

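### The primary table compares who was in VIOLA and in 2019, not how often women were screened, so it cannot test the primary hypothesis

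*Protocol*

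**What the plan says.** - **Question.** Section 4.2.1 asks whether women given Melody have screening mammograms at higher rates than in earlier years. The alternative hypothesis in 10.2 is: "Participation rates in yearly screening mammography with the incorporation of Melody® (examined by geographic location, socio-economic status, race, and ethnicity) will be greater than" the 2019 rates.
- **Comparator.** Section 10.1: "screening mammogram participation rates will be compared to rates reported for the state of Arkansas in 2019".
- **Primary display.** Section 10.4.2 fixes the layout: "Data for primary efficacy endpoints will be presented as follows". The rows are ethnicity, race, income and geography categories. The columns are VIOLA, 2019 and Total. Each VIOLA cell reads "N (% of total for VIOLA"), with the matching entry for 2019. There is one P value per characteristic, four in all.
- **Secondary display.** Section 10.4.3 uses the same columns and cell notation, but its rows, by site, are women who had the mammogram and "Did not follow through with screening mammogram". Section 10.3 describes that analysis as "comparing screening mammography participation rates reported by the clinical site from 2019 to screening mammography participation rates observed after the study".
- **Test.** Section 10.1: "To determine the presence of significant changes, Unpaired T-tests or Mann-Whitney U-test will be used with a significance level set at P < 0.05". Section 10.4.1 applies the same pair of tests to percent change: "For all variables of interest, percent change will be evaluated for statistical significance by Unpaired T-test or Mann-Whitney U-test as appropriate".
- **Sizing.** Sections 5.3 and 10.1 and Appendix L derive 205 for a Pearson chi-square test. The G*Power screens show the equivalent two-sided comparison of proportions, 0.5 against 0.70.

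**The concern.** The hypothesis concerns a rate: women screened divided by women who could have been screened. A table of demographic categories with percentages of the column total contains no such rate. On its natural reading, the P value under each characteristic asks whether the VIOLA column and the 2019 column have the same ethnic, racial, income or geographic make-up.

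This can mislead in both directions. A P value can be small because VIOLA recruited differently from the 2019 reference, which is plausible: section 5.3 encourages minority and medically underserved women to take part, alongside employees and the general public. It also stays null when participation rises equally in every group, which is the effect the study was sized to find.

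The named test does not rescue the table. Percent change has no stated unit of analysis. No P value addresses all participants together, and none of the four is designated as the primary answer.

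**Working it through.** **1. The plan's own figure.** Inputs from Appendix L: p1 = 0.5, p2 = 0.70, two-sided alpha 0.05 (z = 1.960), power 0.80 (z = 0.842), 1:1 allocation.

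n per group = [1.960·√(2·0.6·0.4) + 0.842·√(0.5·0.5 + 0.7·0.3)]² / 0.2² = 93.0, hence 93 per group and 186 in total. 186 × 1.10 = 204.6, hence 205. The stated sizes reproduce, and they belong to a comparison of two participation proportions.

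**2. True effect, same mix.** Take 100 women per column, 10% of them in one category, with 70% against 50% screened.

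- Rate comparison: 70/100 against 50/100, chi-square 8.33, P = 0.004.
- Table as drawn, counting screened women: 7 of 70 against 5 of 50, both 10%, chi-square 0, P = 1.

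Simulated with 103 against 103 enrolled, screened women counted and category shares equal at values from 6% to 50%, the table is significant in about 5% of runs.

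**3. No effect, different mix.** The documents give neither category shares nor 2019 counts, so these are assumptions. Pearson chi-square, uncorrected, VIOLA 15/103 in one category:

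| 2019 column | Share | P |
|---|---|---|
| 6/103 | about 6% | 0.038 (0.065 with continuity correction) |
| 30/500 | 6% | 0.003 |
| 300/5,000 | 6% | 0.0004 |
| 10/103 | about 10% | 0.29 |
| 50/500 | 10% | 0.17 |
| 500/5,000 | 10% | 0.13 |

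Simulated over 20,000 runs (103 against 103 enrolled, 50% participation in both, screened women counted, 2019 share 6%):

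| VIOLA share | Table significant |
|---|---|
| 6% | about 5% |
| 10% | about 12% |
| 15% | about 32% |
| 20% | about 58% |
| 30% | about 92% |

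**4. The named test.** If percent change means one percentage per column, an unpaired t-test has 1 + 1 − 2 = 0 degrees of freedom and cannot be computed. If the unit is the woman's 0/1 outcome, the tests nearly agree. For 65/93 against 47/93 the t-test gives P = 0.0068, Mann-Whitney 0.0072 and chi-square 0.0070. The fault is therefore the undefined unit and the mismatch with the sizing, not the test family.

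**5. Four P values.** If they were independent and any one counted as success, the chance of at least one false positive is 1 − 0.95⁴ = 0.185.

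**The case against.** The strongest reply is that 10.1 and 10.2 already say participation rates are compared, examined by the four characteristics, and that 10.4.2 only describes presentation. On that view the table is an unfinished shell to be completed in an SAP. N is not defined. If it means women screened, with all enrolled women as denominator, the overall VIOLA rate is the sum of the rows.

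Part of this stands. Demographic strata are legitimate under 10.2. But even on the charitable reading no category rate can be obtained and no P value tests the total. The table is also not silent. It fixes rows, cells and the placing of P values, whereas 10.4.3 shows the rows that a rate comparison needs.

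Other objections are fair and limit the claim:

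- The simulated percentages apply a chi-square to the demographic table, whereas the analysis section names t-test or Mann-Whitney. They also assume 103 per column, although section 4.1 gives Melody to every participant. They illustrate the mechanism and do not estimate the protocol's error rate.
- The difference between the sizing test and the named test costs almost nothing on individual 0/1 data.
- The 18.5% needs independence and an any-one-success rule, which the protocol does not state.
- The corrected table needs data that the schedule of events in 7.3.6 does not list. Participant exit-survey item 10 asks intention, item 11 asks only permission for later contact, and provider item 15 counts women who scheduled.

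**Conclusion.** The concern holds: the primary analysis is wrong as written. The display that the protocol fixes for the primary endpoint does not contain the quantity in the primary hypothesis, and the named test has no unit that would supply it.

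Under the sized effect with an unchanged mix, the table has about a 5% chance of significance, against 80% for the rate comparison at 93 per group. Under no effect, its chance of significance depends on how far recruitment differs from the reference. It is about 5% when the shares match and about 92% at 30% against 6%. These figures assume the category shares, the 50% base rate and 103 per column. The direction of the fault does not depend on them.

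**What to change.** 1. **Primary comparison.** State one overall comparison: the proportion of VIOLA women who complete a screening mammogram against the 2019 proportion, two-sided 0.05 as in Appendix L, with a 95% confidence interval. Because 10.2 is worded directionally, say explicitly that the test is two-sided.
2. **Test.** Use a two-proportion chi-square if 2019 counts are available, or a one-sample exact binomial test if only a reported rate is available. In the second case restate the power, since 205 was derived for two groups of 103. With 185 evaluable (205 × 0.9 = 184.5, rounded up) and an assumed 50% reference, exact power is 75% for a true 60%, 83% for 61% and over 99% for 70%.
3. **Table.** Rebuild 10.4.2 on the 10.4.3 pattern, overall and within each category: completed, did not complete, rate, and difference from 2019 with a confidence interval where a 2019 category rate exists.
4. **Wording.** Delete the percent-change sentences for this endpoint in 10.1 and 10.4.1, and define the unit as the woman.
5. **Breakdowns.** Label the four characteristic breakdowns descriptive, or adjust them by Holm's method.

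**Cost.** Table-shell and wording changes and a new power paragraph. Completion must also be captured for each woman with her category attached. The natural source is the site follow-through data that 10.4.3 presupposes; if sites do not record it per woman, it becomes new data collection. Category differences need 2019 category rates, which the documents do not give. Unless Holm-adjusted, the breakdown P values lose confirmatory status.

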The results of the power analysis can be found in Table 1 below. Remember that power analysis calculations using lower effect sizes will tell you that you need larger samples, but these are the calculations easiest to justify. The calculations in the H1 hypothesis (percentage difference in compliance between treated and untreated groups) are the initial power calculation. The second calculation under accounting for 10% drop-out, increases the sample size to account for the drop-out rate you requested. Based on the moderate effect size of $\Delta\% = 20\%$ with a power level of .80, we recommend you recruit 205 participants for this study split evenly between treatment and non-treated groups ($N = 103$ each).

Table 1
Minimum Sample Size Needed for Range of Effect Sizes for Each Study Hypothesis

Hypothesis	Power level	Effect Size			
		Effect	Low	Moderate	
H1: Compliance for Treatment vs Untreated groups	$\Delta\%$		10	20	30
Pearson's Chi-square test of Independence	.80	776	186	78	
	.85	886	214	88	
	.90	1038	248	104	
Accounting for 10% drop-out rate	$\Delta\%$		10	20	30
	.80	854	205	86	
	.85	975	235	97	
	.90	1142	273	114	
Minimum sample size	$\Delta\%$		10	20	30
	.80	854	205	86	
	.85	975	235	97	
	.90	1142	273	114	

Note. Alpha level = .05. The numbers represented here are the total number of participants that would be needed for the sample.

Write-up to include in a methods section (if needed)

An a priori power analysis was conducted using G*Power v3.1.9.2 to determine the minimum sample size required to find significance with a desired level of power set at .80, an alpha (α) level at .05. Based on this analysis, it was determined that a minimum of 205 participants (two groups of 103) were required to ensure adequate power for a Pearson's Chi-square Test of Independence. (Cohen, 1988; Erdfelder, Faul, & Buchner, 1996; Faul, Erdfelder, Lang, & Buchner, 2007).

References

Cohen, J. (1988). Statistical power analysis for the behavioral sciences (2nd ed.). Hillsdale, NJ: Lawrence Erlbaum Associates.

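### The named tests (unpaired t-test or Mann-Whitney on percent change) do not fit a yes/no participation endpoint compared with reported 2019 rates, and are not the test the sample size was computed for

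*Protocol*

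**What the plan says.** Section 10.1 of the protocol sizes the study and names the analysis. For size, a "minimum of 205 participants were required to ensure adequate power for a Pearson's Chi-square Test of Independence". For analysis, "Unpaired T-tests or Mann-Whitney U-test will be used with a significance level set at P < 0.05". Section 10.4.1 applies the same pair of tests to every variable: "percent change will be evaluated for statistical significance by Unpaired T-test or Mann-Whitney U-test as appropriate". No test of proportions appears among the analysis methods in section 10.

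The comparators are reported rates. For the primary endpoint, "screening mammogram participation rates will be compared to rates reported for the state of Arkansas in 2019" (section 10.1). For the secondary endpoint, section 10.3 plans "comparing screening mammography participation rates reported by the clinical site from 2019 to screening mammography participation rates observed after the study". The alternative hypothesis in section 10.2 is that participation "will be greater than participation rates recorded in 2019".

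The primary table in section 10.4.2 has a VIOLA, a 2019 and a Total column. Each VIOLA cell has the form "N (% of total for VIOLA", and there is one P value per characteristic. The site table in section 10.4.3 has two rows, for women who had the mammogram and women who did not.

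Appendix L compares a treated with an untreated group: a "minimum of 205 participants (two groups of 103) were required to ensure adequate power for a Pearson's Chi-square Test of Independence". Its screenshots use proportions 0.50 and 0.70, two-sided alpha 0.05 and power 0.80.

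**The concern.** An unpaired t-test or a Mann-Whitney test needs a sample of values in each of two groups. Percent change is one number per comparison, and a reported rate is one number for 2019. Neither supplies the two samples. The analyst would have to decide, after the data are in, what the observations are, and the answer depends on that decision.

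Two things are at stake. The P value for the primary endpoint may not bear on the hypothesis in section 10.2. The 80% power belongs to a different test in a different layout.

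The protocol names these tests as its method, so this is a rule stated wrongly. It is not a detail left to a statistical analysis plan.

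**Working it through.** **1. Reproduce the sample size.** Inputs from Appendix L: p1 = 0.50, p2 = 0.70, two-sided alpha 0.05, power 0.80, 1:1 allocation. With the mean proportion 0.60,

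n per group = [1.960 × √(2 × 0.60 × 0.40) + 0.842 × √(0.50 × 0.50 + 0.70 × 0.30)]² / 0.20² = (1.358 + 0.571)² / 0.04 = 93.

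The total is 186, and 186 × 1.10 = 204.6, so 205. The stated figure is reproduced, and it belongs to a comparison of two independent proportions.

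**2. The t-test on the table percentages.** With k exclusive categories, each column sums to 100%, so both column means are 100/k. The difference is 0, so t = 0 and P = 1 whatever the data. In 5,000 random pairs of columns for each of k = 2 and k = 5, Student and Welch tests both gave P = 1 to rounding. Two limits apply:
- The race item in the enrollment survey (Appendix D) lets a woman tick more than one race, so that column may exceed 100%. With VIOLA sums of 100 to 115%, the smallest simulated P was 0.36.
- If all percentages in both columns are equal, t is 0/0 and undefined.

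**3. Mann-Whitney on the table percentages.** In a two-row table the columns are (a, 100 − a) and (b, 100 − b). Both are symmetric about 50, so the statistic sits at its null mean and P = 1. This covers ethnicity, geographic location and each site. In five-row tables P is not fixed at 1: it ranged from 0.15 to 1 over 5,000 random pairs, and none fell below 0.05.

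**4. The protocol's own planning effect.** Percentages of 70/30 against 50/50 give P = 1.00 by both tests. Pearson chi-square on matching counts, 65 of 93 against 46 of 93, gives 186 × (65 × 47 − 46 × 28)² / (93 × 93 × 111 × 75) = 8.07, P = 0.0045.

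**5. The same tests on 0/1 data.** If both groups are expanded to one 0 or 1 per woman (same counts), the t-test gives P = 0.0043, Mann-Whitney 0.0046 and chi-square 0.0045. Simulated type I error at a 50% rate with 93 per group was 0.0495 for both the t-test and the two-proportion z-test.

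**6. What the primary table can test.** Its percentages are shares of the column total, so they describe the make-up of each group. They do not give participation within a subgroup. Even a chi-square test on that table would compare composition and would not test H_1.

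**7. Power for a one-sample comparison.** The protocol gives no 2019 rate, so 50% is assumed here. By the normal approximation at two-sided 0.05 and 80% power, the detectable difference is (1.960 + 0.842) × √(0.50 × 0.50 / n):
- n = 186 (evaluable after dropout): 0.103
- n = 205: 0.098

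The exact binomial test with n = 186 at one-sided 0.025, for assumed rates of 0.50 to 0.70, has power 0.78 to 0.87 for a 10-point rise and above 0.999 for a 20-point rise.

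**The case against.** The strongest reply is that no sentence makes the column percentages the observations. Sections 10.4.2 and 10.4.3 say only how results will be laid out. The 2019 columns also have room for counts, and a completed two-row site table determines the 0/1 data. On those data the t-test and chi-square nearly coincide (step 5), so the choice of test would hardly matter.

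Much of this stands. A reader might infer that the plan always returns P = 1, that it cannot detect a rise, or that no P value from it could test H_1. The documents do not support those readings. P = 1 depends on analysing the percentages, is not assured for race, and does not extend to Mann-Whitney in the five-row tables. Where a site supplies 2019 counts, a usable P value can be obtained.

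What does not stand is that the text describes that route. It tests percent change against reported rates. Where counts do exist, a test of proportions is the direct method and the one already used for the sample size.

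**Conclusion.** The point holds as a mismatch between endpoint, comparator, named tests and sample size. Sections 10.1 and 10.4.1 fix two-sample tests of values for a binary outcome compared with reported rates, and the 80% power was computed for a test the analysis section does not use.

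The size depends on how the text is carried out. On the table percentages, the protocol's planned effect of 50% against 70% gives P = 1.00. On data expanded from counts it gives about 0.0045. A plan that allows both answers to the same data needs correcting before analysis.

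The one-sample power figures rest on an assumed 2019 rate treated as known without error. They apply to the whole sample. Subgroups are smaller and will detect only larger differences.

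**What to change.** - **Primary endpoint (10.1 and 10.4.1).** Replace the two tests with an exact one-sample binomial test, with a 95% confidence interval, of the proportion of participants completing a screening mammogram against the 2019 Arkansas rate. Do this overall and within each subgroup listed in section 10.3. State the reference rate and its source before analysis.
- **Sites (10.4.3).** Where a site has 2019 counts, use Pearson chi-square or Fisher's exact test on the two rows already planned.
- **Primary table (10.4.2).** Show completed and not completed within each subgroup, in place of each subgroup's share of the total.
- **Power (5.3, 10.1 and Appendix L).** Restate it for the test adopted. Say whether it is one- or two-sided, because section 10.2 is directional and Appendix L is two-sided.
- **Exit surveys (Appendices J and K).** Do not retain two-sample rank tests for the four-point items. They have no counterpart in the enrollment survey and there is no control group, so no second sample is planned.

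The cost is small changes to wording and one table. The analysis does depend on completed-mammogram data, which sections 10.3 and 10.4.3 already presuppose. The participant survey asks about intention, and the provider survey asks how many women scheduled a mammogram. These passages must be reconciled so that completion is recorded.
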